6.8.5.5 Sample Collection

In consenting patients we will take an extra 3-5 ml of CSF (the exact volume will depend on whether or not the patient is also have CSF taken for leukocyte analysis (see section 6.8.3)). We will ensure no more than the maximum recommended amount of CSF is taken in total (15-17ml)(35). The CSF will be to sequence the pathogen in its entirety. 18ml of blood in EDTA tubes will be taken for the human DNA analysis.

This study will also be funded by FSF funding.

6.9 Substantial Amendment 12 (3/09/2013)

Following interim analysis of the data from the Meningitis NorthWest study (predecessor to UK Meningitis Study) it was discovered that up to 40% of patients with proven meningitis never have a pathogen identified. Therefore, further funding was successfully obtained from the National Institute for Health Research to look into this further.

6.9.1 Qualitative study investigating themes in investigating a case of acute meningitis

One reason pathogens are not found in cases of meningitis is that diagnostic tests and investigations are not performed in a standardized way in cases of meningitis.

Using the already established network of centres (and new ones in the UK Meningitis Study), **semi-structured interviews will be carried out** with clinicians who have recently treated a potential case of meningitis. The clinicians will be identified following cases that are enrolled into the UK Meningitis study. To ensure that the actual work and decisions made by clinicians is captured as accurately as possible, I am proposing to interview clinicians, face to face, as soon as possible after they have treated such patients. The interviews will be carried out to understand the decisions and management of each case.

Additionally, **focus groups** with laboratory staff will explore the acceptability of the introduction of novel technologies for meningitis.

Following local research governance approval identification of the clinicians would be done via the research team recruiting the patients. Clinicians who may be potential participants will be sent a letter of introduction and an information sheet as soon as local governance is obtained in order to ensure that they are aware of the research, can ask relevant questions, and have enough time to consider their participation. This can be sent via a trust wide e-mail. The research nurses within each of the sites will be notified of this component of the Fellowship to ensure that there is clear communication and understanding of the research. The relevant research nurse will be contacted to determine the name of the clinician who initially looked after the patient. They will then be contacted via a letter, information sheet, and completion of a brief 'profile' questionnaire. If possible there will also be a brief follow up phone call. If the participant is agreeable a time and location convenient for them to carry out the interview will be arranged.

Semi-structured interviews will be undertaken and will last between 30 and 45 mins.

Informed consent will be used to ensure participants understand the research and consent to take part. The interviews will explore participants' previous training, speciality, and management of meningitis – using the recent case as an exemplar. Additionally, the introduction of a 'blanket' test all potential causes of meningitis will be discussed to understand any barriers to implementation.

Clinical Staff

To ensure maximum variation 30 semi-structured interviews will be carried out with the medical staff. The clinicians interviewed will be stratified according to speciality and level of seniority, doctors within the first 4 years post qualification (foundation and core medical

trainees); and more senior specialist trainees (ST3 and above). If possible consultant interviews will also be carried out. In addition the interviews will be carried out in both secondary and tertiary care. This information will all be available on the case record form for the patient enrolled. The laboratory staff will also be stratified according to secondary or tertiary care.

To avoid bias any doctors identified on the delegation log for the UK Meningitis Study or NW studies will be ineligible.

Initial interview data produced from semi-structured interviews will be analyzed for emerging themes and further interview questions will be developed if necessary.

Laboratory staff

Focus groups will also be carried out with laboratory staff. One will be in a large teaching hospital and one in a smaller district general. Focus groups will be used in order to access the mixture of laboratory staff (e.g. microbiologists, virologists, biomedical scientists and managers) involved in testing CSF samples.

Analysis

Interviews will be audio recorded and uploaded on to a secure server at the University of Liverpool – password protected. Data will be transcribed by an experienced health services transcribing service. Data will only be seen by the research fellow, [name], her supervisor, [name], and the transcriber. Data will be anonymised and any references which may identify participants by location will be removed. Transcriptions will be checked for accuracy against the original recorded data. Transcribed data will be uploaded on to Atlas TI – computer software which is extensively used by qualitative researchers. The iterative approach will be used on the topic guides for the semi-structured interviews, this means that initial interviews will be analysed and discussed amongst the team, before subsequent interviews, in order to allow any developing or unexpected themes to be incorporated into subsequent versions of the topic guides. Data analysis will follow a grounded theory approach and use the constant comparative method.

Coding, the initial process in the analysis will begin with line-by-line coding on the first four interviews where a code or term(s) that best describes the data will be applied. Incident coding of each of the remaining interviews will then be completed to allow for a more in-depth analysis. During incident coding, each incident will be compared with other incidents in other interviews.

Codes generated will be linked directly to the data. Focused coding, where the codes are collapsed into categories and sub-categories, and finally, modified axial coding, a process of reassembling the data to give coherence to the developing theory.

6.9.2 Molecular studies to improve diagnostics in aseptic meningitis.

Background

The clinical differentiation between different causes of meningitis is difficult. A lumbar puncture is, therefore, necessary to provide cerebrospinal fluid (CSF) to determine the cause. It is not always easy to determine viral from bacterial meningitis without a lumbar puncture, therefore, antibiotics are often given to all suspected cases. As a result, positive cultures in cases of bacterial meningitis are declining. Consequently molecular tests, such as

the polymerase chain reaction (PCR), are now vital in the diagnosis for both viral and bacterial meningitis.

Even with using PCR a significant number of patients with meningitis never have a definitive cause found for their illness. Failure to obtain the correct microbiological diagnosis has been shown to lead to lengthened hospital stays and unnecessary antimicrobials and investigations.

Newer approaches to diagnosis are available

Multiplex PCR utilizes molecular methods to test for several pathogens at once. This means less sample being used, less consumables, reduced handling of the sample and quicker turnaround times. Multiplex PCR has been shown to be cost effective in some conditions. However, a concern with multiplex PCR is that sensitivity can be lost because not all primers work 100% effectively to detect all potential pathogens using a single PCR condition. Nevertheless there have been preliminary reports of comparable, and improved, sensitivity when multiplex has been compared with singleplex.

Multiplex PCR allows for the **rapid and accurate identification** of multiple pathogens at once.

Current laboratory practice in the molecular investigation of CSF is variable:

- In most NHS sites PCR for each potential pathogen is done as a singleplex or duplex reaction (i.e. only one or two pathogens at a time).
- Often the different PCRs are performed in different laboratories e.g. enterovirus PCR might be done at the local laboratory, the bacterial PCR sent to one laboratory and the remaining viral PCRs to another.
- Some laboratories will select the most appropriate investigations based on the initial CSF microscopy whilst others will only test for what is directly requested by the clinician.
- Usually the amount of CSF taken is very small, and with so many different tests in different locations, the sample has often all been used before investigations are completed.

All these permutations mean potential delay in the final diagnosis, or no definitive diagnosis at all. With increasing centralisation of diagnostic laboratories it is likely that more CSF samples will travel further to be tested. Therefore it will be even more important to define what best practice should be with regard to microbiological diagnosis in cases of meningitis. One solution to these problems is for all CSF samples from patients with meningitis to have the same broadrange multiplex PCR covering all common central nervous system (CNS) pathogens. This would make the most of the available sample (because less sample is used in a multiplex test than multiple individual tests), eliminate the sample travelling to several laboratories thus reducing potential false negatives associated with frequent freeze/thawing. It would also counteract the fact that the requesting physician does not always request all of the appropriate tests at the outset.

Methods

Leftover CSF samples will be tested for common CNS pathogens using new commercially available multiplex kits, and also by singleplex PCR for a comprehensive array of pathogens, to evaluate the sensitivity of these kits.

Other molecular methods will also be used on leftover samples to establish if there are any novel pathogens contributing to meningitis in the UK.

MassTag PCR is a form of multiplex PCR that uses primers with tags of different molecular weights to identify the product. The MassTag PCR allows a rapid and sensitive diagnostic platform that can screen up to 30 bacterial, viral and fungal agents.

High throughput sequencing can be used to identify novel pathogens unidentified from conventional PCR techniques. In the few years since the development of high throughput sequencing the costs have decreased drastically and the speed increased.

These methods will be utilised with collaborators in the US and the UK.

Statistical analysis

Confirmed clinical cases (i.e. CSF white cell count >4 cells/ml), expected to be about 60% of all suspected cases, will be analysed by routine conventional testing and by variants of PCR testing as described above.

Using routine conventional testing a proportion 0.6 of confirmed cases leads to successful pathogen detection (data from the Meningitis NorthWest study). The hypothesis states that multiplex PCR testing will increase the proportion of successful pathogen detections to 0.7. The primary analysis will apply McNemar's test to the matched pairs of binary outcomes (routine testing and multiplex PCR). In a secondary analysis, I will simultaneously compare the performances of all four testing methods (standard of care, singleplex and the 2 multiplex PCRs) using a generalized linear mixed model, specifically a logistic regression model with testing method as a fixed effect and patient as a random effect.

The table below shows the power of the primary analysis to detect an increase in the proportion of successful diagnoses from 0.6 to 0.7 when testing at the conventional 5% level of significance. Power is tabulated as a function of the number, N, of suspected cases and the standard deviation, SD, of the patient random effect.

	N				
SD	200	400	600	800	1000
0.0	0.33	0.62	0.8	0.9	0.95
0.2	0.34	0.61	0.79	0.89	0.95
0.4	0.32	0.6	0.78	0.89	0.94
0.6	0.31	0.59	0.75	0.88	0.94
0.8	0.31	0.57	0.75	0.86	0.93
1.0	0.29	0.55	0.73	0.84	0.91

Based on these results, a sample size of 600 suspected cases would be used so as to achieve a power of between 0.73 and 0.80 according to the value of SD, on which there is no prior information.

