7.2 Sample Size

Based on previous retrospective epidemiological studies (Kupila et al and Michael et al) we expect to see the following number of cases.

58	No meningitis	Bacterial Meningitis	Aseptic meningitis	HSV-2 meningitis	VZV	Enterovirus
1066	682	160	223	38	18	58

This is based on Michael et al's study(36) finding 217 patients with suspected CNS infection over a 3 month period in 10 hospitals in the North West of England. 18 of these patients had aseptic meningitis, 13 had purulent meningitis and 55 just had meningism. I have, therefore, extrapolated that there were 86 patients with suspected meningitis (although this may be an underestimate.) Only 5 of the patients with aseptic meningitis had viral PCRs done and 1 of these (20%) was positive for HSV-2. Although this is clearly a small number it is similar to Kupila et al(5) who found 17% of their aseptic meningitis cases had HSV-2. They also found 26% with enterovirus and 8% with VZV.

I have extrapolated the numbers from Michael et al's study to calculate the expected numbers over a year and in 31 centres. I have calculated the expected prevalence of different viruses from the data in Kupila's study.

It is likely that this is an underestimate as it is based on retrospective data.

Using the HES data(3) there were 2741 finished consultant episodes of viral meningitis in England in 2009-2010. Based on the fact that the North West region has 13% of England's population (Census data) we could expect up to 356 cases of viral/aseptic meningitis in one year.

For this type of study approximately 50 patients are needed as a minimum. For comparisons between diagnostics groups (eg herpes meningitis versus bacterial meningitis), a minimum of 25 patients would be needed in each group to have 90% power to show a

difference of one standard deviation in the measure of interest, allowing for approximately 10% drop out. We are likely to have at least this number of patients with herpes meningitis, and probably many more.

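### Section 6.9.2 sizes the multiplex-PCR comparison on an unsourced 60% confirmed share that section 7.2 (36%) does not support, and its power table does not hold the 0.6 to 0.7 effect it names

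*Protocol*

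**What the plan says.** Protocol section 6.9.2 (statistical analysis) restricts the comparison to cases with more than 4 CSF white cells: "Confirmed clinical cases (i.e. CSF white cell count >4 cells/ml), expected to be about 60% of all suspected cases".

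The baseline is sourced: "Using routine conventional testing a proportion 0.6 of confirmed cases leads to successful pathogen detection (data from the Meningitis NorthWest study"). The hypothesis is that "multiplex PCR testing will increase the proportion of successful pathogen detections to 0.7". The test is paired: "The primary analysis will apply McNemar's test to the matched pairs of binary outcomes (routine testing and multiplex PCR").

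A table gives power at the 5% level for N suspected cases (200 to 1000) and for a patient random-effect SD of 0 to 1.0. The section concludes that "a sample size of 600 suspected cases would be used so as to achieve a power of between 0.73 and 0.80", depending on the SD. The N = 600 column reads 0.80, 0.79, 0.78, 0.75, 0.75, 0.73.

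Section 7.2 builds the main study's expected numbers from an earlier retrospective study with 86 suspected meningitis cases: "18 of these patients had aseptic meningitis, 13 had purulent meningitis and 55 just had meningism". Scaled to a year and 31 centres, its table has 1066 suspected cases: 160 bacterial, 223 aseptic and 682 without meningitis.

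**The concern.** Power depends on the number of confirmed pairs, but the target is written in suspected cases. The share that links the two is therefore a design input. Section 6.9.2 puts it at 60% without a source; section 7.2 implies 36% for what looks like nearly the same quantity. If the lower share applied, 600 suspected cases would fall well short of the 360 pairs on which the stated power rests.

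The table also has power falling as the patient random effect grows. For a paired test with both population proportions fixed, more within-patient correlation means fewer discordant pairs and more power. A downward trend suggests that the table is not holding the effect it says it shows.

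**Working it through.** **Inputs.** Confirmed share 0.60 (6.9.2) or 36% (7.2). Detection proportions 0.6 and 0.7, McNemar's test, 5% level (6.9.2). Sidedness is not stated there; two-sided is assumed.

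**Formula.** With discordant probabilities p01 (multiplex only) and p10 (routine only), d = p01 − p10 and s = p01 + p10:

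power = Φ( (d√n − 1.96√s) / √(s − d²) ).

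For SD > 0, p01 and p10 come from integrating a random-intercept logistic model over the patient effect.

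**1. Reproducing the plan's figure.** n = 0.6 × 600 = 360. At SD 0, p01 = 0.7 × 0.4 = 0.28 and p10 = 0.6 × 0.3 = 0.18, so d = 0.10 and s = 0.46. Power = Φ((1.897 − 1.329)/0.671) = Φ(0.847) = 0.80, as tabulated. With 600 pairs it would be 0.95 and with 216 pairs 0.58, so the table does apply the 60% share.

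The table's values for SD > 0 are approximated when the intercepts are fixed at logit(0.6) and logit(0.7), which makes 0.6 and 0.7 conditional on a zero random effect:

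| SD | Protocol, N = 600 | Conditional, 360 pairs | 0.6 and 0.7 held in the population, 360 pairs |
|---|---|---|---|
| 0 | 0.80 | 0.801 | 0.801 |
| 0.2 | 0.79 | 0.799 | 0.805 |
| 0.4 | 0.78 | 0.790 | 0.815 |
| 0.6 | 0.75 | 0.777 | 0.829 |
| 0.8 | 0.75 | 0.759 | 0.846 |
| 1.0 | 0.73 | 0.738 | 0.865 |

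The third column follows the protocol to within 2.7 points. A continuity-corrected test gives 0.781 to 0.712, with all six values within 2 points. The last column moves the opposite way.

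**2. What the table holds fixed.** At SD 1.0 with conditional values 0.6 and 0.7, the population proportions are 0.583 and 0.669, so d = 0.086, with s = 0.395. With the population proportions held, d stays at 0.10 and s falls from 0.46 to 0.387. Power = Φ((1.897 − 1.220)/0.614) = Φ(1.10) = 0.865.

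**3. The confirmed share.** Source counts in 7.2: (18 + 13)/86 = 36.0%. Expected numbers in 7.2: (160 + 223)/1066 = 383/1066 = 35.9%. At 36%, 600 suspected cases give 0.36 × 600 = 216 pairs.

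- SD 0: Φ((1.470 − 1.329)/0.671) = Φ(0.209) = 0.58.
- SD 1.0, table's own model: 0.52.
- SD 1.0, population proportions held: 0.66.

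None of these reaches 0.73. Obtaining 360 pairs at 36% takes 360/0.36 = 1,000 suspected cases.

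**The case against.** **A reader might infer that 0.73 to 0.80 is an arithmetic error.** It is not. The range reproduces from the section's own inputs: 60% confirmed and conditional probabilities. Fixing conditional probabilities is an ordinary convention for a logistic mixed model, which the section names for its secondary analysis. What stands is that the table's description is of a change in the proportion diagnosed, and for SD > 0 that is not what it holds. The departure is conservative, and SD 0 is untouched.

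**A reader might infer that 36% is right and 60% wrong.** The protocol does not show this. The 36% comes from a three-month retrospective study whose 86 suspected cases are a reconstruction, and 7.2 itself warns that its numbers may be too low. Section 6.9.2 was added in 2013, after interim analysis of the predecessor study, and the 60% may rest on newer data, although only the 0.6 detection rate is attributed to that study. The categories also differ somewhat: section 5.1 attaches cell-type and glucose conditions to the aseptic and purulent labels, and unimpaired consciousness to aseptic, so a case with more than 4 cells could carry neither. Against that, the control group is defined by 4 or fewer cells, so the two shares are close in meaning, and a gap of 60% against 36% calls for an explanation.

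**A reader might infer a further loss because only leftover CSF is tested**, given the remark that "the sample has often all been used before investigations are completed". That remark describes routine NHS laboratory practice. The protocol arranges stored CSF for consenting participants and the gifting of leftovers, and gives no loss rate. Some loss is possible, but no figure for it can be supported.

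**The stakes are limited.** This is an added sub-study, nothing stops the cohort's recruitment at 600, and 7.2 expects 1066 suspected cases a year. That makes the correction easy; it does not make the stated power secure at 600.

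**Conclusion.** The concern holds in two parts. First, 600 suspected cases deliver the stated power only if about 60% are confirmed, a share with no source and in conflict with the 36% in section 7.2. If 36% applied, power would be 0.58 at SD 0 and between 0.52 and 0.66 at SD 1.0, depending on how 0.6 and 0.7 are read. These figures are conditional on 36%; the shortfall is possible, not demonstrated.

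Second, for SD > 0 the table shows power for a smaller population difference than the one named (0.086 instead of 0.10 at SD 1.0). At 360 pairs with the named effect, power runs from 0.80 up to about 0.87, so the quoted lower bound of 0.73 is too low if 60% is right.

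The two parts pull in opposite directions, and only the first threatens the sub-study. The figures assume a two-sided 5% uncorrected McNemar test and a normal random intercept on the logit scale. A continuity correction lowers them by up to about 4 points at 216 pairs (0.54 to 0.48 on the table's model).

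**What to change.** - State the target as 360 confirmed cases with complete pairs of results, not 600 suspected cases.
- Recompute the power table with the population proportions held at 0.6 and 0.7, or keep it and label those values as conditional on a zero random effect.
- Give the source of the 60%, reconcile it with the 36% in section 7.2, and restate power at 600 suspected cases for both shares.

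The cost is some rewording and one recomputed table. The stated power at 600 suspected cases becomes less favourable at the 36% share. If that share applied, 360 pairs would need about 1,000 suspected cases, within the 1066 a year that section 7.2 expects from 31 centres.

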6.9.3 Immunology of aseptic meningitis

Over the last decade it has been discovered that autoimmune encephalitis is an important entity that accounts for some of the previously undiagnosed cases of encephalitis. It is feasible that some of the undiagnosed cases of meningitis are not caused by infections but immune phenomena. Therefore, samples that are already being taken as part of the UK Meningitis Study will be utilised to evaluate and describe the immunology of known causes of viral and bacterial meningitis and compared with the unknowns.

6.10 Gifting of samples

Consent will be obtained for all samples taken for genetic analysis to be gifted to the Liverpool Brain Infections Group, University of Liverpool and the rights to intellectual property will be relinquished by the patient and the NHS trust from whence they came.

7 STATISTICAL CONSIDERATION

7.1 Outcome Measures

7.1.1 Primary

Prevalence of Viral meningitis in the North West of England and the contribution of each virus to that.

7.1.2 Secondary

- a. Time to fever resolution
- b. Resolution of acute morbidity (using the TMS)
- c. Incidence of relapse and recurrence
- d. Change in Headache Impact Test over the study period
- e. Quality of Life Assessment (SF36)
- f. Neuropsychological Outcome (ABNAS)
- g. Economic Analyses (EQ5D)
- h. To determine the number of people with aseptic meningitis being offered an HIV test and the proportion of these that are positive.
- i. Pathogen Specific Outcomes
- j. Clinical Predictors of outcome or pathogen.

